3.1.2 Expansion Stage

After the MTD or MAD has been determined for a formulation, pediatric and young adult patients will be enrolled in tumor type cohorts to obtain additional safety, tolerability, and PK data, as well as any preliminary evidence of anti-cancer activity. Pediatric (< 18 years of age) patients will be treated at or below the formulation-specific MTD or MAD identified in the dose-escalation stage of this study. Young adult patients (≥ 18 years of age) will be treated at the recommended adult dose (see [Section 4.3.2](#)).

The Sponsor reserves the right to determine which formulation(s) will be taken forward into the expansion stage and whether enrollment into the expansion stage using tablets (if applicable) will proceed concurrently with or subsequent to dose-escalation for suspension. Enrollment in expansion cohorts may commence after the IMC has reviewed PK and safety data obtained in the dose escalation phase (see [Section 3.1.3](#)).

Each tumor type will be considered a distinct tumor type cohort. Different tumor type cohorts may not all enroll simultaneously. Tumor type cohorts will be chosen after IMC review, prior to inclusion in the expansion stage of the study. Chosen tumor type cohorts for the expansion stage may also include subgroups of tumor types included in the dose-escalation stage, with inclusion based on confirmed (rather than expected) RAS/RAF/MEK/ERK-pathway activation (based on local testing of sample from time of diagnosis or any subsequent timepoint prior to enrollment) with approval of medical monitor). Two phases of response assessment are planned for the expansion stage: an initial response assessment and an additional response assessment (as defined in [Table 6](#) in [Section 6.1](#)). An initial response assessment will be performed after a minimum of 10 patients, treated at the recommended dose for expansion stage, have

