been enrolled in a tumor type cohort and followed for approximately 12 months, to determine whether to expand the cohort for additional response assessment. For purposes of initial response assessment, patients “treated at the recommended dose for expansion stage” includes those patients who initiate therapy at the eventual recommended dose for expansion, whether they are treated during the dose escalation stage or during the expansion stage. Patients who are dose-reduced from the recommended dose due to therapeutic toxicity will still be included for response assessment. Patients in dose-escalation who are treated below the recommended dose for expansion, and subsequently dose-escalated to the recommended dose, will not be included for response assessment.

Cohort expansion will be started once a pre-established number of responses for that tumor type are confirmed (per [Table 6](#)). A decision to pursue additional enrollment in a tumor type cohort may be approved by the Sponsor or Medical Monitor before the initial response assessment. Cohort expansion, including the number of patients needed for the additional response assessment, will take into account practical considerations (e.g., enrollment feasibility), preclinical findings, biomarker analysis, safety profiles, and any other relevant information. A study schema for the expansion stage is displayed in [Figure 2](#).

If the frequency of Grade 3 or 4 toxicities or other unacceptable toxicities at the initial dose level in the expansion stage suggest that this dose is intolerable, accrual at that dose level will be halted. Consideration will then be given to enrolling patients at a lower dose level.

The Sponsor may decide to stop enrollment of patients ≥ 18 years of age at any time during the study to ensure adequate enrollment of patients < 18 years of age. To meet study completion criteria below, the Sponsor may restrict enrollment of patients ≥ 10 years of age if too few patients < 10 years of age have been enrolled.

The Sponsor intends to stop study enrollment once all of the following criteria are met:

- The dose-escalation phase of both tablet and suspension formulations are complete
- At least 20 patients < 18 years of age have been treated with study drug
- At least one tumor type cohort has completed response assessment (either initial response assessment or additional response assessment)
- At least 10 patients < 10 years of age have been treated with study drug

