6.1 DETERMINATION OF SAMPLE SIZE

For the dose-escalation stage, the sample size is based on the dose-escalation rules described in the study design section of this document. Explicit power and Type I error considerations were not factored into the design, as the dose-escalation stage was designed to obtain preliminary safety and PK information for the study drug.

To make a preliminary assessment of the efficacy of the study drug, two phases of response assessment are planned for the expansion stage: an initial response assessment and an additional response assessment. Taking into account historical control ORRs for each pediatric tumor type, the minimum number of patients in the initial

response assessment and the minimum number of responders needed for advancement to the additional response assessment were calculated and are presented by tumor type in [Table 6](#). The selection of tumor type cohorts for additional response assessment, as well as the number of patients needed for the additional response assessment, will also take into account practical considerations (e.g., enrollment feasibility), biomarker analysis, safety profiles, and any other relevant information. Similar consideration will be given to other rare pediatric tumor types that are enrolled in the study and not included in [Table 6](#). No formal hypothesis testing is planned in this study.

Table 6 Sample Size and Responder Requirements for Initial Response Assessment

Tumor Type (relapsed/refractory)	Historical Control Overall Response Rate (%)	Initial Response Assessment	
		Minimum No. of Patients Enrolled	Minimum No. of Responders Needed for Tumor Type Cohort Expansion
Melanoma	20%	10	3
Neuroblastoma	18%	10	3
Rhabdomyosarcoma	10%	10	2
Non-rhabdomyosarcoma soft tissue sarcoma	10%	10	2
High-grade glioma ^a	12%	10	2
Low-grade glioma ^b	20%	10	3

^a Gururangan et al. 2010; Warren et al. 2012; Fouladi et al. 2013; MacDonald et al. 2013.

^b Packer et al. 2009; Bouffet et al. 2012; Yalon et al. 2013.

Overall, approximately 70 patients will be enrolled in the study.

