6.5.1 Primary Efficacy Endpoints

The co-primary endpoints for efficacy are ORR and PFS.

An objective response is defined as a complete or partial response on two consecutive occasions ≥ 4 weeks apart, as determined by the investigator using mINRC for patients with neuroblastoma, RANO criteria for patients with HGG, RANO criteria for patients with LGG, and RECIST v1.1 for patients with other tumors. ORR is the percentage of patients who are determined to have an objective response. Patients with no post-baseline tumor assessments will be counted as non-responders. ORR and

corresponding 95% exact confidence interval (CI), using the Blyth-Still-Casella method, will be summarized overall and by tumor type cohort.

PFS is defined as the time from initiation of study drug to the first documented occurrence of disease progression, as determined by the investigator, or death from any cause, whichever occurs first. Data for patients without disease progression or death will be censored at the date of the last tumor assessment at which the patient was known to be progression-free or, if no tumor assessment is performed after the baseline visit, at the date of initiation of study drug. The Kaplan-Meier approach will be used to estimate median PFS. The 95% CI of the median PFS will be estimated using Brookmeyer and Crowley method. Subgroup analysis of PFS by tumor type cohort will be conducted as appropriate.

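### For a tumor cohort that advances, the cohort ORR includes the responses that let it advance, and no unbiased estimate is planned beside it (minor).

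*Combined protocol and SAP*

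**What the plan says.** Section 3.1.2 sets the first step: "An initial response assessment will be performed after a minimum of 10 patients, treated at the recommended dose for expansion stage, have" (the sentence goes on to require entry into one cohort and about 12 months of follow-up). It then gives the rule for going on: "Cohort expansion will be started once a pre-established number of responses for that tumor type are confirmed". A cohort that misses its number stops enrolling. Section 6.1 describes the Table 6 figures as including the "minimum number of responders needed for advancement to the additional response assessment". Typical rows are "Melanoma 20% 10 3", "Neuroblastoma 18% 10 3" and "Rhabdomyosarcoma 10% 10 2" (historical rate, patients, responders). Low-grade glioma has the melanoma values, non-rhabdomyosarcoma sarcoma has the rhabdomyosarcoma values, and high-grade glioma has 12%, 10 and 2.

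Section 3.1 allows up to 30 further patients per cohort. The actual number is left open, and Section 3.1.2 lets the sponsor or Medical Monitor approve further enrollment before the first look.

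For the analysis, Section 6.5 uses every patient who received any study drug. Section 6.5.1 gives one ORR with an exact interval "using the Blyth-Still-Casella method", overall and by cohort. Neither section says how the two steps are combined, reports them separately or adjusts for the selection. Section 6.1 states that no formal hypothesis test is planned.

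**The concern.** A cohort that advances under the rule has a first-step responder count cut off from below: low counts have been removed. Putting that count into the cohort ORR raises its expected value above the true rate, conditional on advancing. The interval is computed as if the sample size had been fixed.

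The plan has no test, so the ORR and its interval are the evidence on activity, and Table 6 supplies a benchmark that readers will have in view. The cohorts that expand are also the ones most likely to be described as active. At stake is whether a reader of an expanded cohort can tell how much of the observed rate comes from the patients who triggered the expansion.

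**Working it through.** **Inputs.** First step n1 = 10, and historical rate p0 and threshold r from Table 6 (Section 6.1). Second step n2 is at most 30 (Section 3.1) and not fixed, so 5, 10, 20 and 30 are shown. The true rate p is not given. It is assumed equal to p0 in the base case, then 10, 20 and 30 points higher. The rule is assumed to be applied strictly at n1 = 10.

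**Table 6 thresholds.** The column headed "Minimum No. of Responders Needed for Tumor Type Cohort Expansion" reads 3 / 3 / 2 / 2 / 2 / 3. No formula, alpha or power is given, so it cannot be formally reproduced. The smallest r for which P(X ≥ r | 10, p0) is below 0.5 matches all six rows, but the plan does not state that rule.

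**Expected pooled ORR given advance.** With X1 ~ Bin(10, p) and n2 independent later patients:

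E[ORR | advance] = (E[X1 | X1 ≥ r] + n2·p) / (10 + n2), where E[X1 | X1 ≥ r] = 10p · P(Bin(9, p) ≥ r − 1) / P(Bin(10, p) ≥ r).

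Melanoma, p = 0.20, r = 3:
- P(Bin(10, 0.2) ≥ 3) = 0.3222.
- P(Bin(9, 0.2) ≥ 2) = 1 − 0.1342 − 0.3020 = 0.5638.
- E[X1 | advance] = 2 × 0.5638 / 0.3222 = 3.50, that is 35.0%.
- With 30 more: (3.50 + 6.0) / 40 = 23.75%. With 10 more: (3.50 + 2.0) / 20 = 27.5%.

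Results with the true rate equal to the historical rate:

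| Cohort | p0 | r | P(advance) | First step given advance | Pooled, 10 more | 20 more | 30 more |
|---|---|---|---|---|---|---|---|
| Melanoma, low-grade glioma | 20% | 3 | 32.2% | 35.0% | 27.5% | 25.0% | 23.75% |
| Neuroblastoma | 18% | 3 | 26.3% | 34.3% | 26.2% | 23.4% | 22.1% |
| Both sarcoma cohorts | 10% | 2 | 26.4% | 23.2% | 16.6% | 14.4% | 13.3% |
| High-grade glioma | 12% | 2 | 34.2% | 24.0% | 18.0% | 16.0% | 15.0% |

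The bias is +3.0 to +4.1 points with 30 more patients, +4.0 to +5.4 with 20, +6.0 to +8.2 with 10 and +8.0 to +10.9 with 5. For the later patients alone the expected ORR is p, so their bias is 0.

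**Higher true rates, 30 more patients.** The bias is +1.7 to +2.5 points at p0 + 10, +0.8 to +1.4 at p0 + 20, and +0.3 to +0.6 at p0 + 30.

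**Interval.** Clopper-Pearson stands in for the planned method, with 30 more patients and true rate = p0. Coverage given advance is 94.4% to 95.8%. The chance that the lower limit exceeds p0 is 4.2% to 5.6%, against 1.6% to 2.0% for an unselected sample of 40.

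**Accuracy.** Root mean squared error given advance, pooled against later patients alone (for the latter, √(p(1 − p)/n2)):
- true 20%, r = 3, 10 more: 10.5 against 12.6 points;
- true 40%, r = 3, 10 more: 10.2 against 15.5;
- true 10%, r = 2, 30 more: 5.47 against 5.48.

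**The case against.** The strongest reply is that the study is exploratory. Section 6.1 plans no test, Section 6.7.2 describes the study as hypothesis-generating, and the historical rates serve only to set the expansion thresholds. A reader might infer that selection inflates a planned comparison with the historical rate. The documents do not support that: no such comparison is specified, so there is no error rate to inflate. This part of the reply stands.

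A reader might also infer that an expanded cohort should be judged on its later patients only. That does not follow. In the settings computed, the pooled estimate has a root mean squared error no larger than that of the later patients alone, often clearly smaller. In small rare-tumor cohorts, giving up that precision for unbiasedness is a debatable trade.

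Three further points stand as limits:
- The rule is not rigid. Enrollment may be extended before the first look, and feasibility, biomarker and safety considerations also count; where the threshold does not drive the decision, the bias falls toward 0.
- The direction depends on the conditioning. Averaged over stopped and advanced cohorts at true rate = p0, with 30 patients added on advancing, the plain ORR is biased downward by 2.6 to 3.6 points.
- A split at the go decision does not fit the protocol. Patients may enroll before that decision without being counted in it. Patients started below the expansion dose are excluded from the threshold count in Section 3.1.2 but included in the efficacy population in Section 6.5.

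The first-step ORR is already an interim analysis under Section 6.7.1, so the rest could sometimes be found by subtraction. That works only when both figures cover the same patients, which Sections 3.1.2 and 6.5 do not ensure. None of these points supplies an unbiased estimate in the planned output.

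**Conclusion.** The point holds as a minor one. For a cohort that advances under Table 6, the ORR implied by Sections 6.5 and 6.5.1 is biased upward conditional on advancing, and the plan puts no unbiased estimate beside it. The bias is modest with a full second step, larger with a small one (which the plan permits), and small when the drug is clearly better than the historical rate.

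This rests on three assumptions: the two steps are pooled, which is inferred; the threshold is applied at 10 patients; and the true rate lies in the range shown. Patients started below the expansion dose, if included, would dilute the bias. Coverage stays near 95% in the case checked, so the interval is not the problem. The effect is on how the point estimate of an expanded cohort is read. It also arises only if some cohort is expanded, which the plan leaves open.

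**What to change.** In Section 6.5.1, for each expanded cohort, keep the pooled ORR and exact interval and add the same two figures for:
- (i) patients counted in the initial response assessment;
- (ii) all other patients in the cohort who started at the recommended expansion dose, whether enrolled before or after the go decision.

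State that the pooled estimate includes the data used to select the cohort, and that any descriptive reading against the Table 6 historical rate should show (ii) beside the pooled figure. Do not require the reading to rest on (ii) alone, since (ii) is unbiased but less precise. Note also that (i) and (ii) need not add up to the pooled count if patients started below the expansion dose are in the cohort.

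The cost is extra table rows per expanded cohort and a wide interval for (ii). Design, sample size and patient care do not change.

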6.5.2 Secondary Efficacy Endpoints

The secondary efficacy endpoints are DOR and OS.

For patients who achieve an objective response, DOR is defined as the time from the first tumor assessment that supports the patient's objective response to the time of disease progression, as determined by the investigator, or death from any cause, whichever occurs first. Data for patients without disease progression or death will be censored at the date of the last tumor assessment at which the patient was known to be progression-free or, if no tumor assessment is performed after the baseline visit, at the date of initiation of study drug. The Kaplan-Meier approach will be used to estimate median DOR. The 95% CI of the median DOR will be estimated using Brookmeyer and Crowley method. Subgroup analysis of DOR by tumor type cohort will be conducted as appropriate.

OS is defined as the time from initiation of study drug to death from any cause. Patients who are alive at the data cutoff date will be censored at the date the patient was last known to be alive. The Kaplan-Meier approach will be used to estimate median OS. The 95% CI of the median OS will be estimated using Brookmeyer and Crowley method. Subgroup analysis of OS by tumor type cohort will be conducted as appropriate.

6.6 EXPLORATORY ANALYSES

6.6.1 Biomarker Analyses

Levels of potential PD biomarkers (including but not limited to p-MEK, p-ERK, and Ki67) will be measured in tumor tissue collected at baseline, on treatment, and at the time of disease progression. These samples will be analyzed for changes in biomarker levels in response to exposure to cobimetinib.

Plasma and archival tumor tissue samples will be collected at baseline and analyzed for non-inherited and inherited biomarkers (including but not limited to *BRAF* mutations, *BRAF* fusions, *RAS* mutations, and *NF1* mutations) that may be correlated with

response or resistance to MEK inhibition or with severity of adverse effects associated with MEK inhibition.

A modified ORR will be used for LGG and is defined as the percentage of patients with measurable disease who have a complete, partial, or minor response on two consecutive occasions ≥ 4 weeks apart, as determined by the investigator using RANO criteria for LGG.

ORR for LGG will also be assessed using RECIST v1.1 and is defined as the percentage of patients with measurable disease who have a complete or partial response for on two consecutive occasions ≥ 4 weeks apart, as determined by the investigator.

Diffusion activity and metabolic activity before and after cobimetinib treatment will be analyzed in available tumor MRI scans and PET scans, respectively.

6.6.2 Acceptability Survey

Analyses will be descriptive, enumerating the number of patients that selected each answer choice. Analyses will be conducted separately for patients receiving suspension and patients receiving tablets.

6.7 INTERIM ANALYSES

6.7.1 Planned Interim Analyses

Interim efficacy analyses will be conducted whenever a tumor type cohort has enrolled the 10 patients required for initial response assessment and patients have been followed for approximately 12 months.

6.7.2 Optional Interim Analyses

Given the hypothesis-generating nature of this study, the Sponsor may choose to conduct additional interim efficacy analyses. The decision to conduct an optional interim analysis and the timing of the analysis will be documented in the Sponsor's trial master file prior to the conduct of the interim analysis. The interim analysis will be performed and interpreted by Sponsor study team personnel.

7. DATA COLLECTION AND MANAGEMENT

7.1 DATA QUALITY ASSURANCE

The Sponsor will be responsible for the data management of this study, including quality checking of the data. Data entered manually will be collected via EDC through use of eCRFs. Sites will be responsible for data entry into the EDC system. In the event of discrepant data, the Sponsor will request data clarification from the sites, which the sites will resolve electronically in the EDC system.

The Sponsor will produce an EDC Study Specification document that describes the quality checking to be performed on the data. Central laboratory data and IWRS data will be sent directly to the Sponsor, using the Sponsor's standard procedures to handle and process the electronic transfer of these data.

eCRFs and correction documentation will be maintained in the EDC system's audit trail. System backups for data stored by the Sponsor and records retention for the study data will be consistent with the Sponsor's standard procedures.

7.2 ELECTRONIC CASE REPORT FORMS

eCRFs are to be completed through use of a Sponsor-designated EDC system. Sites will receive training and have access to a manual for appropriate eCRF completion. eCRFs will be submitted electronically to the Sponsor and should be handled in accordance with instructions from the Sponsor.

All eCRFs should be completed by designated, trained site staff. eCRFs should be reviewed and electronically signed and dated by the investigator or a designee.

At the end of the study, the investigator will receive patient data for his or her site in a readable format on a compact disc that must be kept with the study records. Acknowledgement of receipt of the compact disc is required.

7.3 SOURCE DATA DOCUMENTATION

Study monitors will perform ongoing source data verification to confirm that critical protocol data (i.e., source data) entered into the eCRFs by authorized site personnel are accurate, complete, and verifiable from source documents.

Source documents (paper or electronic) are those in which patient data are recorded and documented for the first time. They include, but are not limited to, hospital records, clinical and office charts, laboratory notes, memoranda, evaluation checklists, pharmacy dispensing records, recorded data from automated instruments, copies of transcriptions that are certified after verification as being accurate and complete, microfiche, photographic negatives, microfilm or magnetic media, X-rays, patient files, and records kept at pharmacies, laboratories, and medico-technical departments involved in a clinical trial.

Before study initiation, the types of source documents that are to be generated will be clearly defined in the Trial Monitoring Plan. This includes any protocol data to be entered directly into the eCRFs (i.e., no prior written or electronic record of the data) and considered source data.

Source documents that are required to verify the validity and completeness of data entered into the eCRFs must not be obliterated or destroyed and must be retained per the policy for retention of records described in Section [7.5](#).

To facilitate source data verification, the investigators and institutions must provide the Sponsor or its representatives direct access to applicable source documents and reports for trial-related monitoring, Sponsor audits, and IRB/EC review. The study site must also allow inspection by applicable health authorities.

7.4 USE OF COMPUTERIZED SYSTEMS

When clinical observations are entered directly into a study site's computerized medical record system (i.e., in lieu of original hardcopy records), the electronic record can serve as the source document if the system has been validated in accordance with health authority requirements pertaining to computerized systems used in clinical research. An acceptable computerized data collection system allows preservation of the original entry of data. If original data are modified, the system should maintain a viewable audit trail that shows the original data as well as the reason for the change, name of the person making the change, and date of the change.

